1. OBJECTIVES

Study Hypothesis #1: Perampanel treatment reduces peritumoral hyperexcitability in newly diagnosed high grade glioma (HGG).

Study Hypothesis #2: Perampanel treatment in newly diagnosed HGG is associated with improvement in seizure control.

1 Study Design

This pilot study (Cohort 1) in participants with newly discovered radiologic lesions consistent with HGG evaluates the effect of perampanel on peritumoral hyperexcitability, measured by the rate of high frequency oscillations on intra-operative electrocorticography (ECoG), compared to a contemporary observational control group (Cohort 2) of participants undergoing ECoG and standard peri-operative seizure management. To estimate the effect size of early perampanel treatment on ongoing seizure control, participants in Cohort 1 will be maintained post-operatively on perampanel, adjusted on a clinical basis until evidence of disease progression (or maximum of 12 months), and compared to participants in Cohort 2 receiving standard of care post-operative seizure management.

1.1 Primary Objectives

Primary Objective: Measure the effect of perampanel on peritumoral hyperexcitability using intraoperative ECoG at the time of initial glioma resection. We will analyze high frequency oscillations (80-500 Hz) as a biomarker of peritumoral hyperexcitability and epileptogenicity. The rate of high frequency oscillations over 10 minutes of recording in the tumor margins will be compared between perampanel treated participants (Cohort 1) and control participants (Cohort 2).

1.2 Secondary Objectives

Secondary Objective: Estimate the clinical effect of perampanel maintenance therapy on seizure control. We will measure seizure-free rates between the time of initial glioma resection and radiographic tumor progression (up to a maximum of 12 months), in participants continued on perampanel post-operatively (Cohort 1) compared to control participants (Cohort 2).

2. BACKGROUND

2.1 Study Disease(s)

This study evaluates peritumoral hyperexcitability and tumor-associated seizures in HGG, including WHO Grade III anaplastic astrocytoma and WHO Grade IV glioblastoma. Seizures are seen in up to 60% of patients with HGG,¹ and contribute to decreased quality of life.² While seizures generally occur earlier in the disease course, up to half of patients with HGG and

glioma-associated epilepsy continue to have uncontrolled seizures despite anti-seizure medications.^{3,4} To date, there are no evidence-based guidelines or widely accepted standards of care regarding the use and duration of anti-seizure medications to prevent seizures in this population, or evidence to guide the choice of one anti-seizure medication over another.⁵

Different glioma subtypes have unique propensities for the development of seizures, suggesting that gliomagenesis and epileptogenesis are inter-related, and that variable mechanisms may be involved.^{6,7} Among the mechanistic pathways with the most experimental evidence is dysregulation of glutamatergic signaling, whereby excitatory glutamatergic signaling pathways are upregulated in the glioma microenvironment, and contribute to excitotoxicity.^{7,8} Preclinical studies demonstrate an increase peritumoral glutamatergic hyperexcitability mediated through multiple mechanisms, including activation of the system x_c^- cystine-glutamate transporter, and AMPA-receptor mediated neuron-glioma synaptic activity.^{9,10} Recent evidence indicates that glioma growth is dependent on glutamatergic neuronal activity, mediated by the release of neuroligin-3 and the downstream activation of PI3K-mTOR signaling.^{8,11,12} Glutamate release from glioma cells leads to the development of neuronal-gliial synaptic connections, hyperexcitability, and further tumor growth in a positive feedback loop. Thus, excessive excitatory signaling appears to be a shared mechanism underlying tumor growth and epileptogenesis, and a promising therapeutic target.

The clinical relevance of peritumoral hyperexcitability in management of glioma-associated epilepsy remains uncertain, however early evidence linking glioma growth with excessive neuronal synaptic activity offers the possibility of targeted therapies with enhanced efficacy.^{8,10} Through its anti-glutamatergic actions, the AMPA-receptor antagonist perampanel has been shown to inhibit glioblastoma growth in vitro,¹³ and has been associated with radiologic glioma responses in a small clinical case series.¹⁴ In a small series patients with glioma-associated epilepsy refractory to at least two anti-seizure medications, perampanel resulted in seizure freedom in half of cases.¹⁵ Therefore, perampanel treatment may have the potential to inhibit neuronal activity-dependent glioma progression and improve seizure control through reduction of peritumoral hyperexcitability.

2.2 IND Agent(s)

N/A

2.3 Other Agent(s)

Perampanel is a non-competitive AMPA-receptor antagonist, which obtained initial FDA approval in 2012 for the adjunctive treatment of focal and generalized epilepsy, and gained FDA approval in 2017 for use as monotherapy for the treatment of focal epilepsy. In three placebo-controlled trials of perampanel in drug-resistant focal epilepsy, a combined response rate ($\geq 50\%$ seizure reduction) was observed in 19%, 29%, 35%, and 35% of patients treated with placebo, 4mg, 8mg, and 12mg, respectively.¹⁶

With high bioavailability ($\sim 100\%$) and blood-brain barrier penetration,¹⁷ and long half-life (average 105 hours), effective levels in the brain can be achieved after a single loading dose.

Doses up to 32mg have been used safely in humans, and a median dose of 6mg has been found to terminate status epilepticus after a median of 24 hours.¹⁸ The minimum therapeutic dose is 4mg daily. In placebo-controlled trials, the rate of perampanel discontinuation due to adverse effects in subjects receiving doses of 4mg was 3%, compared to 5% receiving placebo.¹⁶ Given these data, perampanel will be given as a single loading dose of 6mg on the day prior to resection, then continued at 4mg daily. Additional dose adjustments will be made on a clinical basis, as per institutional standards. Dose and schedule modifications will not affect the objectives of this study.

Perampanel is extensively metabolized via primary oxidation (primarily mediated by CYP3A4/5 and to a lesser extent by CYP1A2 and CYP2B6) and sequential glucuronidation. Perampanel is eliminated mostly in the feces (48%) and to a lesser extent in the urine (22%). Moderate and strong CYP3A4 inducers decrease plasma levels of perampanel by approximately 50-67%.¹⁶

2.4 Rationale

Preclinical studies of glioma-associated epilepsy demonstrate an increase in peritumoral glutamatergic hyperexcitability mediated through multiple mechanisms, including activation of the system x_c^- cystine-glutamate transporter,^{9,19} and AMPA-receptor mediated neuron-glioma synaptic activity.^{10,12} Through its anti-glutamatergic actions, perampanel has demonstrated both anti-tumor and anti-seizure effects in vitro and in vivo.^{13,14} In one series of patients with glioma-associated epilepsy, perampanel was associated with a reduction in tumor volume in half of cases, correlated with plasma drug levels.¹⁴ Additionally, objective seizure responses of 75-100% have been reported in small series of patients with drug-resistant glioma-associated epilepsy treated with perampanel after the failure of at least two other anti-seizure medications.^{14,15} Thus, perampanel treatment may have the potential to inhibit neuronal activity-dependent glioma progression and improve seizure control through reduction of peritumoral hyperexcitability. Since glioma progression is independently associated with increased seizure frequency,^{1,20} this study aims to correlate perampanel use with reduction in peritumoral hyperexcitability at initial diagnosis, and estimate the effect of maintenance therapy on seizure control up to the time of progressive disease.

2.5 Correlative Studies Background

Interictal high frequency oscillations (HFOs) measured using intracranial EEG have been previously associated with the seizure onset zone,²¹⁻²³ and resection of regions generating HFOs associated with improved seizure outcomes in retrospective analyses of surgical epilepsy series.²⁴ High frequency activity has also been demonstrated in peritumoral regions in intra-operative ECoG recordings,^{10,25} representing a promising biomarker of peritumoral epileptogenicity. As described in Section 1, the primary objective is a correlative study testing the hypothesis that perampanel will reduce peritumoral HFOs through a mechanism of targeting excessive peritumoral glutamatergic activity.

Glioma-related excitotoxicity is primarily attributed to excessive glutamate release and impaired re-uptake in the peritumoral environment.²⁶ In-vivo microdialysis in the tumor margins of high

grade gliomas have demonstrated a metabolic profile involving decreases in glucose, and increases in lactate/pyruvate ratios, glutamate, and glycerol concentrations.²⁷ However, whether specific electrophysiologic signatures reflect these local metabolic tissue changes remains uncertain. This protocol involves a correlative tissue analysis of peritumoral metabolites and principal excitatory/inhibitory neurotransmitters to define excitotoxic changes in relation to electrophysiologic excitability. Molecular analysis will be performed using a mass spectrometry method that bypasses the needs for systemic injections of molecular probes required for traditional molecular imaging methods.

Mass spectrometry is a well-established analytical technique used to identify and characterize molecules based upon their accurate mass. More specifically here, we will use Matrix Assisted Laser Desorption Ionization (MALDI) mass spectrometry imaging (MSI) to directly map the distribution of metabolites and neurotransmitters in tissue sections with correlation to histopathology evaluation of the tissue.

3. PARTICIPANT SELECTION

3.1 Eligibility Criteria

- 3.1.1 Participants must have radiologic evidence of anaplastic astrocytoma or glioblastoma multiforme within 14 days of enrollment.
- 3.1.2 Participants must have measurable disease, defined as at least one lesion that can be accurately measured in at least one dimension as ≥ 10 mm (≥ 1 cm) with CT or MRI. See Section 11 (Measurement of Effect) for the evaluation of measurable disease.
- 3.1.3 Age ≥ 18 years.
- 3.1.4 ECOG performance status ≤ 2 (Karnofsky $\geq 60\%$, see Appendix A).
- 3.1.5 Participants must have adequate organ and marrow function as defined below:
 - leukocytes $\geq 3,000/\text{mcL}$
 - absolute neutrophil count $\geq 1,500/\text{mcL}$
 - platelets $\geq 100,000/\text{mcL}$
 - total bilirubin \leq institutional upper limit of normal (ULN)
 - AST(SGOT)/ALT(SGPT) $\leq 3 \times$ institutional ULN
 - glomerular filtration rate (GFR) ≥ 30 mL/min/1.73 m² (see Appendix B)
- 3.1.6 Human immunodeficiency virus (HIV)-infected participants on effective anti-retroviral therapy with undetectable viral load within 6 months are eligible for this trial.
- 3.1.7 For participants with evidence of chronic hepatitis B virus (HBV) infection, the HBV viral load must be undetectable on suppressive therapy, if indicated.
- 3.1.8 Participants with a history of hepatitis C virus (HCV) infection must have been treated

and cured. For participants with HCV infection who are currently on treatment, they are eligible if they have an undetectable HCV viral load.

- 3.1.9 Participants with a prior or concurrent malignancy whose natural history or treatment does not have the potential to interfere with the safety or efficacy assessment of the investigational regimen are eligible for this trial.
- 3.1.10 Participants with known history or current symptoms of cardiac disease, or history of treatment with cardiotoxic agents, should have a clinical risk assessment of cardiac function using the New York Heart Association Functional Classification. To be eligible for this trial, participants should be class 2B or better.
- 3.1.11 The effects of perampanel on the developing human fetus are unknown. For this reason and because some anti-seizure medications are known to be teratogenic, women of child-bearing potential and men must agree to use adequate contraception (hormonal or barrier method of birth control; abstinence) prior to study entry and for the duration of study participation. Should a woman become pregnant or suspect she is pregnant while she or her partner is participating in this study, she should inform her treating physician immediately.
- 3.1.12 Ability to understand and the willingness to sign a written informed consent document.

3.2 Exclusion Criteria

- 3.2.1 Participants with brain metastases due to confounding effects on the study objectives.
- 3.2.2 History of allergic reactions attributed to compounds of similar chemical or biologic composition to perampanel.
- 3.2.3 Participants receiving any medications or substances that are moderate or strong inducers of CYP3A4 are ineligible. Because the lists of these agents are constantly changing, it is important to regularly consult a frequently-updated medical reference. As part of the enrollment/informed consent procedures, the participant will be counseled on the risk of interactions with other agents, and what to do if new medications need to be prescribed or if the participant is considering a new over-the-counter medicine or herbal product.
- 3.2.4 Participants with uncontrolled intercurrent illness.
- 3.2.5 Participants with psychiatric illness/social situations that would limit compliance with study requirements.

- 3.2.6 Pregnant women are excluded from this study because perampanel is an anti-seizure agent with the potential for teratogenic or abortifacient effects. Because there is an unknown but potential risk for adverse events in nursing infants secondary to treatment of the mother with perampanel, breastfeeding should be discontinued if the mother is treated with perampanel.
- 3.2.7 Participants with a history of suicide attempt or current active suicidal ideation with intent as defined by Columbia Suicide Severity Rating Scale (C-SSRS) type 4-5, due to the potential for suicidal ideation with the use of all anti-seizure medications.
- 3.2.8 Participants who are unable to swallow pills.
- 3.2.9 Participants with tumor associated seizures greater than one month before planned surgery.
- 3.2.10 Participants currently receiving treatment with more than one anti-seizure medication.

3.3 Inclusion of Women and Minorities

Both men and women of all races and ethnic groups are eligible for this trial.

4 REGISTRATION PROCEDURES

In order to maximize enrollment into the pilot study over a short time, and given the difficulty in recruiting participants within a narrow pre-operative time window, we will perform concurrent recruitment into the single arm pilot group (Cohort 1) and a contemporary observational control group (Cohort 2). Eligible participants will be informed and provided the consent forms for both study groups, and those who have no preference will be enrolled in the cohort with the smaller current enrollment, while those who express a preference will be enrolled into the cohort of their preference (up to a maximum enrollment of 10 per cohort). This will enable eligible participants to be enrolled who decline to be randomized. We do not anticipate a systemic bias in endpoints using this method of enrollment, as potentially confounding factors (described in Section 13) are not expected to influence enrollment preferences, although we cannot completely exclude it.

4.1 General Guidelines for DF/HCC Institutions

Institutions will register eligible participants in the Clinical Trials Management System (CTMS) OnCore. Registrations must occur prior to the initiation of any protocol-specific therapy or intervention. Any participant not registered to the protocol before protocol-specific therapy or intervention begins will be considered ineligible and registration will be denied.

An investigator will confirm eligibility criteria and a member of the study team will complete the protocol-specific eligibility checklist.

Following registration, participants may begin protocol-specific therapy and/or intervention.

Issues that would cause treatment delays should be discussed with the Overall Principal Investigator (PI). If the subject does not receive protocol therapy following registration, the subject must be taken off study in the CTMS (OnCore) with an appropriate date and reason entered.

4.1 Registration Process for DF/HCC Institutions

Applicable DF/HCC policy (REGIST-101) must be followed.

4.2 General Guidelines for Other Investigative Sites

N/A

4.3 Registration Process for Other Investigative Sites

N/A

5. TREATMENT PLAN

5.1. Treatment Regimen

Perampanel will be given every day until meeting the study endpoint(s). Reported adverse events and potential risks are described in Section 7. Appropriate dose modifications are described in Section 6. Other anti-seizure medication(s) may be administered during perampanel maintenance therapy as clinically indicated.

Cohort 1

Participants who are already receiving an anti-seizure medication pre-operatively for treatment of tumor-associated seizures will receive their last dose at least 36 hours before scheduled surgery start-time, and then will be switched to perampanel. The loading dose of perampanel will be 6mg by mouth, given on the day prior to surgery (12-36 hours before scheduled start time), followed by a maintenance dose of 4mg by mouth once a day. Participants will be requested to maintain a drug diary of each dose of medication. The drug diary will be returned to clinic staff at the end of each month.

Study day	Perampanel dose
Day 1 (load)	6mg
Day 2+ (maintenance)	4mg

Cohort 2

Perioperative and post-operative seizure management will be performed by the primary treating physician(s) according to institutional standards.

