9.2.1.1. Collection of Specimens

No changes will be made to the routine clinical care of patients in this study. All aspects of the surgical management including preoperative and postoperative care will be carried out per the standard of care. Specimens will be collected for the study during tumor resection. The study

will not affect the manner or quantity of tissue removed. In addition to the bulk tumor specimen as routinely sent, numerous small specimens will be collected during the resection using tumor forceps at sampling positions registered to pre-operative MRI images using a navigation system (General Electric Instatrak or BrainLab Vector Vision). All specimens will be sent to the BWH Tissue Biorepository. When the Tissue Biorepository has confirmed that enough tissue has been collected to make a diagnosis, specimens will be made available MALDI MSI.

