13.1. Study Design/Endpoints

Pilot Study: Preliminary Study

- Primary objective: Compare rates of peritumoral HFOs (mean number of HFOs per minute) between participants treated with perampanel versus standard of care.
- Secondary objective: Compare time to seizure recurrence between participants treated with perampanel versus standard of care up to the time of HGG progression.
- Maximum total accrual: 10 participants in Cohort 1, 10 participants in Cohort 2.
- Sample size justification: Using the mean HFO rate across participants receiving standard of care (Cohort 2) as the normalized ineffective rate ($P_1=1.0$), we define a target effective rate for the treatment arm (Cohort 1) of $P_2=0.60$. Using a two sample power calculation, the intended sample size of 10 participants in each cohort will provide 82.5% power to detect a true 40% or greater reduction in the normalized mean HFO rate with perampanel compared to standard of care ($\alpha=0.05$, two-sided).
- Statistical methods for primary objective: The primary endpoint is the mean number of HFOs per minute. This will be averaged across participants in each cohort, and compared using the Mann-Whitney U test (two-sided, $\alpha=0.05$). In sensitivity analyses, we will compare HFO rates between cohorts stratified by potential confounding variables, including temporal lobe tumor location, IDH1/2 mutation, and pre-operative seizures.
- Statistical methods for secondary objective: The secondary endpoint is the time to first post-operative seizure. Time to first post-operative seizure will be estimated in time-to-event analysis from the date of surgery using the Kaplan-Meier method. Comparison

between Cohort 1 and Cohort 2 will be performed using the log-rank test ($\alpha=0.05$). In sensitivity analyses, we will compare time to first post-operative seizure between cohorts stratified by potential confounding variables, including temporal lobe tumor location, extent of resection (gross total vs subtotal resection), presence of IDH1/2 mutation, and presence of pre-operative seizures.

- Data processing and statistical analysis will be performed using R 3.5.3 (The R Foundation for Statistical Computing).
- These results will be used to support or refute the hypothesis that perampanel has targeted anti-epileptogenic activity in glioma-associated epilepsy, and may inform the design and feasibility of future clinical studies of targeting the glutamatergic pathway in this patient population.

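### Only Cohort 1 must stop a prior anti-seizure medication before ECoG, so a null HFO result could not refute an effect of perampanel

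*Combined protocol and SAP*

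**What the plan says.** Section 5.1 treats the two cohorts differently before the ECoG. In Cohort 1, participants on an ASM for tumor-associated seizures "will receive their last dose at least 36 hours before scheduled surgery start-time, and then will be switched to perampanel". For Cohort 2 it says "Perioperative and post-operative seizure management will be performed by the primary treating physician(s) according to institutional standards". It also says "Other anti-seizure medication(s) may be administered during perampanel maintenance therapy as clinically indicated". Section 3.2.10 excludes only people on more than one ASM, so users of a single ASM can enter either cohort.

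Section 9.2.1.1, on specimen collection, says "All aspects of the surgical management including preoperative and postoperative care will be carried out per the standard of care".

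Section 13.1 declares the primary contrast as HFO rate under perampanel versus standard of care. The power statement is built "Using the mean HFO rate across participants receiving standard of care (Cohort 2) as the normalized ineffective rate", set at 1.0, with a Cohort 1 target of 0.60. The sensitivity analyses of HFO rate stratify by temporal-lobe site, IDH1/2 status and seizures before surgery; ASM exposure at ECoG is not listed. On interpretation, the section states: "These results will be used to support or refute the hypothesis that perampanel has targeted anti-epileptogenic activity in glioma-associated epilepsy".

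**The concern.** Hypothesis 1 and the primary objective (sections 1 and 1.1) ask what perampanel itself does to peritumoral hyperexcitability. For participants with a prior ASM, section 5.1 changes two things at once in Cohort 1: perampanel is started and the other drug is stopped. Nothing in the plan requires that stop in Cohort 2.

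The protocol itself treats other ASMs as able to move the endpoint. Section 9.2.1 hypothesizes that hyperexcitability is related to tissue levels of ASMs in general, section 9.2.1.2 measures levetiracetam as well as perampanel, and Aim 3 of the correlative analysis in 13.1 relates ASM signal to HFO rate. Yet the standard-of-care mean is labelled the ineffective rate, and no analysis of the primary endpoint uses ASM exposure.

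What is at stake is the reading of a null or weak result. Under the interpretive sentence in 13.1 it would count against perampanel, when it could equally reflect one active drug replacing another.

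**Working it through.** **1. The plan's own figure.** Inputs from 13.1: 10 per cohort, two-sided alpha 0.05, rates 1.0 and 0.60, power 82.5%. No SD is given, so the figure cannot be reproduced, only solved backwards. It needs an SD of about 0.309 of the control mean (normal approximation) or 0.292 (noncentral t, 18 df). For the planned Mann-Whitney test, simulated normal data with SD 0.28 give 81.9%. Reading 1.0 and 0.60 as proportions does not recover it (62.5% pooled, 73.3% unpooled, 86.5% arcsine, 36.7% Fisher). An SD of 0.292 is used below.

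**2. What each participant has on board at ECoG.**

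| At enrolment | Cohort 1 | Cohort 2 |
|---|---|---|
| One ASM, for tumor seizures | Perampanel; prior ASM stopped at least 36 h before surgery | Institutional standards; no stop required |
| One ASM, for prophylaxis | Perampanel; switch rule does not address the ASM | Institutional standards |
| No ASM | Perampanel | Institutional standards |

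Only the first row carries a mandated difference in the other drug. Its share of the 20 participants is not given.

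**3. Direction.** Set the drug-free mean at 1 and assume perampanel alone gives 0.60. This redefines the 40% as a cut versus no drug, which is not how 13.1 defines it. Let f be the share whose ASM is stopped in Cohort 1 and continued in Cohort 2, and r that ASM's proportional effect on HFOs, gone by ECoG in Cohort 1. Both are assumptions.

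- Cohort 1 mean = 0.60; Cohort 2 mean = 1 − f·r
- Difference = 0.40 − f·r
- Apparent reduction = 1 − 0.60/(1 − f·r)

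For any positive f·r up to 0.40 the difference shrinks toward zero.

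**4. Illustration.** Worked row, f = 0.5 and r = 0.2: Cohort 2 mean = 1 − 0.10 = 0.90; 0.60/0.90 = 0.667, a 33.3% reduction. The noncentrality is 0.30/(0.292 × √(2/10)) = 2.30, giving 58.4% power. With no attenuation it is 0.40/(0.292 × √(2/10)) = 3.06, giving 82.5%.

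| f | r | Cohort 2 mean | Apparent reduction | Power (t) |
|---|---|---|---|---|
| any | 0 | 1.000 | 40.0% | 82.5% |
| 0.25 | 0.1 | 0.975 | 38.5% | 77.5% |
| 0.25 | 0.2 | 0.950 | 36.8% | 71.7% |
| 0.25 | 0.4 | 0.900 | 33.3% | 58.4% |
| 0.5 | 0.1 | 0.950 | 36.8% | 71.7% |
| 0.5 | 0.2 | 0.900 | 33.3% | 58.4% |
| 0.5 | 0.4 | 0.800 | 25.0% | 30.5% |

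At f = 0.6, 0.60/0.88 = 0.68 (32% reduction, r = 0.2) and 0.60/0.76 = 0.79 (21%, r = 0.4). The 60% in section 2.1 is an upper figure for seizures in high grade glioma, not for ASM use at ECoG. Larger f is not shown: it would have to count prophylactic users, whom the switch rule does not withdraw.

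**5. The same gap on the plan's own scale.** If 0.60 is relative to Cohort 2, perampanel's cut versus no drug must be 1 − 0.60 × (1 − f·r) to reach it: 1 − 0.60 × 0.90 = 46% at f = 0.5, r = 0.2, and 1 − 0.60 × 0.80 = 52% at r = 0.4. The power statement for the strategy contrast is untouched; what changes is what that contrast says about perampanel.

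**6. The planned stratifier.** Among participants with pre-operative seizures, the required stop still follows cohort, so stratifying does not remove it. The strata are also small: for a 40% reduction, 5 per arm gives about 48% power (t) or 36% (Mann-Whitney), and 7 per arm about 65% or 57%.

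**7. An offset.** The 36 h is a minimum, with no check of clearance. Section 5.3.2 starts maintenance 24 h after a load given 12 to 36 h before surgery, so maintenance can begin up to 36 − 24 = 12 h beforehand, and 5.1 allows other ASMs from then. Residual or added ASM in Cohort 1 would work against the attenuation above.

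**The case against.** The declared and powered contrast is perampanel versus standard of care. For that question the switch is part of the intervention, and the 40% target is already net of whatever Cohort 2 receives. This stands: the strategy comparison is legitimate, and the table in the working is not a correction to the 82.5%. It does not reach the interpretive sentence in 13.1, which claims more than a strategy comparison.

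Cohort 2's practice is unspecified, and section 2.1 says there is no widely accepted standard for ASM use. This also stands: continuation in Cohort 2 is an inference.

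Other information is planned. Concurrent drugs are captured (section 5.4 and the study calendar), and Aim 3 relates ASM signal to HFOs. But neither medication record asks for hours from last dose to ECoG, and the tissue study is optional and exploratory.

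Section 9.2.1.1 can be read as covering only tissue sampling. That is fair, but its wording about pre-operative care is broad and does not mention the switch in 5.1.

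A reader might infer that the trial can neither support nor refute its hypothesis. The documents do not support that: if the stopped ASM lowers HFOs, the bias runs against perampanel, so a lower Cohort 1 rate remains supportive. A reader might also infer that the effect is overstated if Cohort 1 prophylaxis users keep their ASM. That needs comparable Cohort 2 participants with no ASM, which is nowhere stated; if both keep it, the contrast is a balanced add-on.

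**Conclusion.** The asymmetry is real and no analysis of the primary endpoint addresses it. Among prior ASM users the primary result estimates a switch-to-perampanel strategy against standard care. A positive result would still favour perampanel, subject to the preference-based allocation in section 4. A null or attenuated result could not refute an effect of the drug.

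The conclusion on direction rests on two assumptions: that the stopped ASM lowers HFOs, and that Cohort 2 continues it. The size cannot be determined from the documents. For f from 0.25 to 0.5 and r from 0.1 to 0.4, a true 40% cut versus no drug would show as 38.5% down to 25%, with power from 77.5% to 30.5% at the back-solved SD. It would be wrong to infer that the plan's power claim is in error by that amount, because the plan's target is set against standard of care.

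This is a limit on interpretation in a 20-participant non-randomized pilot, and a cheap improvement. It does not invalidate the design.

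**What to change.** 1. In 13.1, state that the primary result estimates a perampanel-switch strategy versus standard of care, and that a null result does not by itself refute perampanel activity.
2. On the case report form for both cohorts, record each ASM and the hours from its last dose to ECoG. This should be set up before surgery, since timing may not be reliably recoverable afterwards.
3. Prespecify descriptive HFO estimates by ASM use at enrolment (yes/no), taken before any change driven by cohort. Do not restrict instead to participants with no ASM within 36 h of ECoG: that would keep switched Cohort 1 seizure patients and drop their Cohort 2 counterparts who stayed on treatment, leaving a comparison confounded by seizure history.
4. Reconcile 5.1 with 9.2.1.1 on whether pre-operative care is changed, and make clear which Cohort 1 participants may have another ASM on board at ECoG, including prophylactic users. Which clinical rule applies is for the sponsor and investigators to settle.

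The cost is protocol wording and one timing item added to medication data already collected. No extra participants or procedures are needed. The downside is small strata, fit only for description, and a narrower headline claim.
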